4.2.3.6 Analysis of exploratory variables

Analysis of all exploratory endpoints will be performed in the ITT analysis set unless otherwise specified. Baseline values, the values at each visit, and changes from baseline values will be summarized for percentiles of body weight, percentile of height, and BMI by treatment.

Change in BMI from baseline Visit 2 (Week 0) to Visit 7 (Week 24), Visit 10 (Week 52), and to each intermediate visit

A similar MMRM modeling approach will be implemented to compare changes in BMI between treatment groups from Visit 2 (Week 0) to Week 24, and each intermediate visit.

The least squares mean (LSM) change from baseline and SE bar by visit will be presented in a figure by treatment group. The p-value for the difference between treatment groups by visit will also be provided in the figure.

The observed values and change from baseline will be summarized by visit using descriptive statistics (mean, median, standard deviation, minimum, maximum). This will be provided separately for both the ITT analysis set during the controlled assessment period and for the subset of ITT patients who received open-label EQW during the extension period for the Treatment period.

Change in BMI percentile from baseline Visit 2 (Week 0) to Visit 7 (Week 24), Visit 10 (Week 52), and to each intermediate visit

Observed and change from baseline in BMI percentile will be summarized by visit using descriptive statistics (mean, median, standard deviation, minimum, maximum). This will be provided separately for both the ITT analysis set during the controlled assessment period and for the subset of ITT patients who received open-label EQW during the extension period for the Treatment period.

Change in body weight percentile and height percentile from baseline Visit 2 (Week 0) to Visit 7 (Week 24), Visit 10 (Week 52), and to each intermediate visit

The height and weight percentile will be determined based on the standardized growth chart for boys and girls (developed by the National Center for Health Statistics in collaboration with the National Center for Chronic Disease Prevention and Health Promotion). For this purpose, the percentile values for weight and height will be calculated using the growth chart tables on CDC³ using the raw data available for weight and height. The growth chart tables for boys' and girls' population will be used separately for 3rd to 97th percentile.

A MMRM modeling approach will be implemented to compare changes in body weight percentile, and height percentile between treatment groups from Visit 2 (Week 0) to Week 24, and each intermediate visit.

The least squares mean (LSM) change from baseline and SE bar by visit will be presented in figures by treatment group. The p-value for the difference between treatment groups by visit will also be provided in the figure.

The observed values and change from baseline for body weight percentile and height percentile will be summarized by visit using descriptive statistics (mean, median, standard deviation, minimum, maximum). This will be provided separately for both the Evaluable analysis set during the controlled assessment period and for the subset of Evaluable patients who received open-label EQW during the extension period for the Treatment period.

4.2.4 Safety and tolerability analysis

Analysis of safety data will be performed using the Safety analysis set. All safety and tolerability variables such as examination of AEs, clinical laboratory measurements, physical examination findings, vital signs, and antibodies to exenatide will be summarized descriptively by treatment groups. Observations post-rescue will be included for safety analyses.

For all safety endpoints summary tables will be presented by visit to Week 52, and where applicable also for the 10-week follow-up, for each treatment group. Continuous variables (observed, change from baseline, laboratory and vital signs parameters) will be summarized by visit using number, mean, median, standard deviation, minimum and maximum for each

treatment group. Categorical variables (incidence of AEs, antibodies, physical examination, Tanner pubertal stage) will be summarized by visit in the form of number and percentage (%) for each treatment group.

A listing of Tanner pubertal stage data will also be provided.

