5.5.3 Rescue Treatment

A loss of glycemic control observed by either 1) an increase from baseline in HbA1c values by 1.0% or more that is confirmed at a subsequent clinic visit scheduled at the Investigator's discretion, or 2) fasting glucose value ≥ 250 mg/dL or random blood glucose > 300 mg/dL for 4 days during a 7-day period measured by home SMBG, and confirmed by fasting or random glucose test within the same range of values (measured by local laboratory) at a clinic visit, will result in rescue treatment. A clinic visit to confirm the values obtained by home SMBG or fasting/random glucose tests must take place within 2 weeks following the aforementioned self-measurements.

Patients meeting rescue criteria will be treated with antihyperglycemic therapy (eg, insulin) by the Investigator or referred to their treating physician to seek conventional antihyperglycemic intervention. Patients meeting these criteria should remain in the study and continue to receive study medication, at the discretion of the Investigator. AstraZeneca will not supply the rescue medication. Acute decompensation due to an intercurrent illness treated briefly with insulin will be allowed for 2 weeks, if longer this should be considered as rescue treatment.

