4.1.4 Handling of data post rescue medication

Instances of patients meeting rescue criteria and subsequently receiving rescue medication will be recorded by sites as defined in Section 3.6.3.

A loss of glycemic control observed by either 1) an increase from baseline in HbA1c values by 1.0% or more that is confirmed at a subsequent clinic visit scheduled at the Investigator's discretion, or 2) fasting glucose value ≥ 250 mg/dL or random blood glucose > 300 mg/dL for 4 days during a 7-day period measured by home self-monitored blood glucose (SMBG), and confirmed by fasting or random glucose test within the same range of values (measured by local laboratory) at a clinic visit, will result in initiation of rescue medication. A clinic visit to confirm the values obtained by home SMBG or fasting/random glucose tests must take place within 2 weeks following the aforementioned self-measurements.

Patients meeting rescue criteria will be treated with antihyperglycemic therapy (e.g., insulin) by the Investigator or referred to their treating physician to seek conventional antihyperglycemic intervention. Patients meeting these criteria should remain in the study and continue to receive study medication, at the discretion of the Investigator. Acute decompensation due to an intercurrent illness treated briefly with insulin will be allowed for 2 weeks, if longer this should be considered as rescue medication.

Derivation of variables at initiation of rescue medication

Efficacy

In general, efficacy data are to be continuously collected during the glycemic rescue therapy. For all efficacy endpoints, except the plasma exenatide concentration endpoint, data collected after the first administration of rescue therapy will be excluded from the descriptive statistical summary and inferential statistical analyses.

However, data collected after initiation of rescue medication will be included in several sensitivity and supportive analyses for the primary analysis to provide a comprehensive view of the treatment effect (see more details in Section 4.2.3.4).

Safety

Because patients can continuously receive study medication concurrent with the rescue therapy, all safety data collected during the rescue medication treatment period will be summarized and analyzed together with those collected prior to the rescue therapy.

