4.2.4.7 Hypoglycemia

All summaries of hypoglycemic events will be presented for both the controlled assessment period (Safety analysis set) and the extension period (subset of Safety patients who received open-label EQW during the extension period). Hypoglycemic events will be presented as events occurring after the first dose of study medication through the end of the treatment plus 7 days.

The number and percentage of patients with hypoglycemic events, per the HYAEBO eCRF, along with the number of events will be summarized by severity (mild, moderate, severe or unknown) defined as follows,

Mild: Usually transient, requires no special treatment, and does not interfere with the patient's daily activities.

Moderate: Usually causes a low level of inconvenience or concern to the patient and may interfere with daily activities but is usually ameliorated by simple therapeutic measures.

Severe: Requires the assistance of another person to obtain treatment (e.g., intravenous glucose, intramuscular glucagon, or oral carbohydrate) for the event.

Additionally, hypoglycemia will be programmatically classified as major, minor, or other hypoglycemia as follows,

- Major hypoglycemia is defined as:

An event that results in loss of consciousness, seizure, or coma (or other mental status change consistent with neuroglycopenia in the judgment of the Investigator or physician), and which resolves after administration of glucagon or glucose

Or

An event that requires third party assistance to resolve because of severe impairment in consciousness or behavior (whether or not symptoms of hypoglycemia are detected by the patient) and is associated with a plasma or capillary glucose concentration of <3 mmol/L (54 mg/dL)

- Minor hypoglycemia is a non-major hypoglycemia event that has symptoms consistent with hypoglycemia and had a glucose value of <3 mmol/L (54 mg/dL) prior to treating the episode.
- If a hypoglycemia event does not meet the criteria for a major or minor event described above, it will be classified as other.

The number and percentage of patients with hypoglycemic events, along with the number of events will be summarized by major/minor classification.

Hypoglycemic events will also be programmatically classified into three levels⁶ according to severity:

- Level 1: A glucose alert value of 3.9 mmol/L (70 mg/dL) or less.
- Level 2: A glucose level of <3.0 mmol/L (<54 mg/dL) is sufficiently low to indicate serious, clinically important hypoglycemia

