- Level 3: Severe hypoglycemia, as defined by the ADA^{7, 8}, denotes severe cognitive impairment requiring external assistance for recovery

The number and percentage of patients with hypoglycemic events based on the aforementioned classification, along with the number of events will be summarized by level.

The number and percentage of patients with any hypoglycemic event by baseline insulin and sulfonylurea use will be summarized according to the following categories:

- Any (includes patients with and without insulin/sulfonylurea use at baseline)
- Insulin and sulfonylurea use at baseline
- Insulin only
- Sulfonylurea only

- No insulin or sulfonylurea

Key patient information for hypoglycemic events will be presented.

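### The hypoglycemia tables pool events before and after rescue, which may be insulin, and no planned controlled-period table separates them, so unequal rescue can shift the EQW-placebo comparison

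*SAP*

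**What the plan says.** SAP 4.2.4 gives the general rule: "Observations post-rescue will be included for safety analyses". SAP 4.1.4 repeats it: "all safety data collected during the rescue medication treatment period will be summarized and analyzed together with those collected prior to the rescue therapy". The reason given there is that patients can stay on study medication while receiving rescue.

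SAP 4.2.4.7 fixes the counting window for hypoglycemia without a cut at rescue: "Hypoglycemic events will be presented as events occurring after the first dose of study medication through the end of the treatment plus 7 days". The tables are by severity, by major/minor/other class and by three glucose-based levels. One further table concerns background therapy: "The number and percentage of patients with any hypoglycemic event by baseline insulin and sulfonylurea use will be summarized". None uses rescue status.

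On what rescue is, SAP 4.1.4 says: "Patients meeting rescue criteria will be treated with antihyperglycemic therapy (e.g., insulin) by the Investigator". Protocol 5.5.3 says the same. On what follows, SAP 4.1.4 says: "Patients meeting these criteria should remain in the study and continue to receive study medication, at the discretion of the Investigator".

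SAP section 5 adds two facts. The protocol defines no hypoglycemia analysis, so 4.2.4.7 is the only rule. The observed number of patients rescued at Week 24 was low; no count and no split by arm is given.

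**The concern.** For most adverse events, keeping post-rescue data is unremarkable. Hypoglycemia is different because the rescue drug can cause the event directly. Rescue is triggered by loss of glycemic control (a confirmed HbA1c rise of 1.0% or more, or confirmed high glucose). If EQW lowers HbA1c as the sample size assumes (a difference of -0.7%), one would expect more rescue on placebo. Events caused by rescue insulin would then be credited mainly to the placebo arm and would narrow any EQW excess.

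The baseline insulin/SU table does not resolve this. A patient on neither drug at baseline who starts insulin as rescue stays in the row for patients on neither drug, and later events are counted there. SAP 3.6.4 also allows an insulin increase in a baseline insulin user to be classed as rescue, so the insulin rows are affected too.

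At stake is how clearly the 24-week comparison with placebo can be read. Safety and tolerability over those 24 weeks is a primary objective (Protocol 2.1), although hypoglycemia is not named there or in the list of safety endpoints.

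**Working it through.** The plan gives no expected hypoglycemia or rescue rate, so it has no figure of its own to reproduce on this point. Its 74% power concerns HbA1c and has no bearing here.

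**Inputs from the documents.** 77 patients randomized 5:2 (Protocol 12.7): 77 × 5/7 = 55 on EQW and 77 × 2/7 = 22 on placebo. One patient is therefore 1/22 = 4.5 points on placebo and 1/55 = 1.8 points on EQW.

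**Assumed inputs (illustration only).**
- p, the risk of any hypoglycemia apart from rescue: 15% EQW and 5% placebo, a true excess of 10.0 points.
- r, the share rescued: three scenarios.
- q, the added risk once rescued, the same in both arms: 0.1 to 0.5.

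**Formula.** The tabulated share with any event is 1 − (1 − p)(1 − rq). Pooling therefore adds (1 − p)rq to an arm.

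**One case in full.** One of 22 placebo patients rescued, no EQW patient rescued, q = 0.5:
- Placebo: 1 − 0.95 × (1 − 0.04545 × 0.5) = 1 − 0.95 × 0.97727 = 7.16%.
- EQW: unchanged at 15.00%.
- Tabulated excess: 15.00 − 7.16 = 7.84 points, a loss of 2.16.

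| Rescued, EQW / placebo | q | EQW % | Placebo % | Tabulated excess, points |
|---|---|---|---|---|
| 0 / 1 of 22 | 0.1 | 15.00 | 5.43 | 9.57 |
| 0 / 1 of 22 | 0.5 | 15.00 | 7.16 | 7.84 |
| 4% / 14% | 0.1 | 15.34 | 6.33 | 9.01 |
| 4% / 14% | 0.5 | 16.70 | 11.65 | 5.05 |
| 10% / 30% | 0.1 | 15.85 | 7.85 | 8.00 |
| 10% / 30% | 0.5 | 19.25 | 19.25 | 0.00 |

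Given the SAP's remark that rescue was low, the first two rows are the more relevant. The last two show what heavy, unequal rescue would do.

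**Direction.** EQW looks safer when (1 − p)rq is larger on placebo than on EQW. With a common q and these values of p, that holds whenever placebo patients are rescued more often.

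**Scale.** The standard error of the difference at these risks is √(0.15 × 0.85/55 + 0.05 × 0.95/22) = 6.7 points, well above the loss of 0.4 to 2.2 points with one placebo rescue.

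**Comparison within the SAP.** In 4.2.4.4 the eGFR model is run once without and once with data after rescue. The primary HbA1c analysis is cut at rescue, and a supplementary analysis includes the later data. Hypoglycemia, on which rescue acts directly, has only the pooled version.

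**The case against.** The strongest reply is that pooling is a reasoned choice. Rescued patients may stay on study medication, so counting all on-treatment events is a treatment-policy summary, and it matches the rule for treatment-emergent adverse events in SAP 4.2.4.1. This stands. A reader might infer that the all-events tables are wrong and that pre-rescue tables should replace them; the documents do not support that. The trial studies EQW as an adjunct to insulin among other therapies, so events on EQW plus rescue insulin are relevant. Replacement would also shorten placebo follow-up more if placebo is rescued more. Applied to the extension, it would drop the EQW hypoglycemia data of placebo patients rescued before Week 24.

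A second reply is that the information is partly visible. The SAP plans a rescue summary and listing, time to rescue, total daily insulin by visit and key patient information for hypoglycemic events. With few rescues, a reader could match individual events by hand. This stands in part: nothing commits to flagging post-rescue events or to counting them by arm.

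A third reply is that grouping by baseline insulin/SU use is a proper pre-randomization subgroup. That is correct. The table is not defective; it simply answers a different question.

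**Conclusion.** The gap is real but modest. No planned controlled-period table separates hypoglycemia before rescue from hypoglycemia after it, so the effect of EQW cannot be told apart from the effect of rescue insulin. If placebo patients are rescued more often, the comparison is shifted towards making EQW look safer.

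Two stronger readings go beyond the documents. A reader might infer that the bias certainly runs one way. More rescue on placebo is an inference from the trigger and an effective drug, and rescued EQW patients taking insulin on top of EQW have their events counted in the EQW arm. A reader might also infer that the shift is large enough to cancel a true excess. Two added placebo patients would be 2/22 = 9.1 points, but that needs both to have their first event after rescue and no EQW patient to do so. The documents give no rescue count by arm and no split by rescue drug (insulin is only an example), and they call rescue at Week 24 low. The tables are also descriptive, with no test to overturn.

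The conclusion concerns the controlled period only, since all patients receive EQW afterwards. It is a cheap improvement to interpretation rather than the correction of an error.

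**What to change.** Keep the all-events tables in SAP 4.2.4.7. For the controlled assessment period only, add the same tables by arm (severity, major/minor, level, baseline insulin/SU use) restricted to events before first rescue as dated under SAP 3.6.4. Show pre-rescue exposure time or exposure-adjusted rates beside the percentages, because the cut shortens follow-up unequally if rescue is unequal. Flag post-rescue events in the key patient information for hypoglycemic events.

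The cost is one extra set of tables, using a rescue date that is already derived. The downside is shorter follow-up for rescued patients in the added version, which the exposure column makes visible. No event is lost from the main tables.

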4.2.4.1 Adverse event analysis

Adverse events (AE) will be classified in accordance to the Medical Dictionary for Regulatory Activities (MedDRA) dictionary. All adverse events will be coded using the latest available version of MedDRA by the database lock.

Treatment-emergent AEs (TEAE) are defined as AEs occurring after the first dose of study medication through the end of the treatment plus 7 days (or + 90 days for SAEs and other clinically significant or related AEs), including AEs collected after patients initiate glycemic rescue therapy.

AEs occurring after Study Termination but considered by the Investigator as clinically significant and as related to study medication or study procedure, and SAEs occurring within 90 days of the last administration of study medication or EQW if in the extension phase will be recorded on the AE eCRF and reported in the AE listing.

Any AE that is recorded as the reason for study discontinuation will be considered an adverse event leading to discontinuation (DAE) regardless of the date recorded. All DAEs will be reported regardless of when they occurred. Note, any AE that is a DAE under these rules will also count as an AE when reporting.

Off-treatment AEs will be defined for the following:

- Treatment completers to Week 52: An AE that occurs between Week 52 to Week 62 and starts the day after last dose of open-label EQW + 7 days (or + 90 days for SAEs and other clinically significant or related AEs). Only patients completing study medication to Week 52 will be considered. Patients completing study medication to Week 52 but who withdraw prior to Week 62 will also be included.
- Premature discontinuation: An AE that starts the day after last dose of study medication + 7 days (or + 90 days for SAEs and other clinically significant or related AEs), for patients who discontinue study medication before Week 24 or Week 52.

AEs for the combined periods are those that occur during the Treatment period or post-treatment.

AEs with a start date prior to the first administration of study medication will be classified as pre-treatment (non-treatment emergent).

AEs with a stop date prior to the date of the first administration of study medication will be classified as pre-treatment (non-treatment emergent) AEs.

In case of missing AE severity, AE causality, or AE seriousness, a worst-case approach will be used. For AE missing severity, the AE will be considered severe; for missing causality, the

AE will be considered as possibly-related to study medication; for missing seriousness, the AE will be considered serious.

On-treatment AEs (TEAEs) will be summarized for 24-week controlled assessment period and 28-week extension period as defined below. Off-treatment AEs for treatment completers to Week 52 will be tabulated where required. Off-treatment AEs for patients who prematurely discontinued will be listed only.

An overall summary of number and percentage of patients experiencing at least 1 TEAE will be presented for EQW and PBO. The summary will be presented by study period (controlled assessment period and extension period). A summary of AEs during the Treatment period for patients with actual treatment EQW during the controlled assessment period will be provided. The AE summary will include the number and percentage of patients experiencing any AE, any SAE, any AE related to treatment per Investigator's discretion, any AE leading to treatment discontinuation, any AE leading to study withdrawal, and any fatal AE.

Additionally, all TEAEs will be summarized for each treatment group as follows:

- AEs summarized by SOC, PT, maximum intensity (Mild, Moderate, Severe), causality (Not related, Related), action taken, and outcome.
- SAEs summarized by SOC and PT, maximum intensity (Mild, Moderate, and severe), causality (Not related, Related).
- AEs leading to treatment discontinuation summarized by SOC and PT.
- Frequent AEs (AE with at least 5% incidence in any treatment) summarized by preferred term.
- Non-serious frequent AEs summarized by SOC and PT.
- Potentially immune-related AEs summarized by antibody status (positive versus negative), SOC and PT.
- Potentially immune-related AEs summarized by antibody titer (higher: ≥ 625 versus low: < 625), SOC and PT.
- Potentially immune-related injection site-related AEs summarized by SOC and PT.

Summaries by maximum intensity will be presented separately for the controlled assessment period (Safety analysis set) and extension period (subset of Safety patients who received open-label EQW during the extension period). All other AE summary tables will be presented by study period in a single table.

Potentially immune-related AEs will be identified using the PTs given in [Appendix B4](#).

Injection site-related AEs will be identified using AEs within higher-level term "Injection site reactions".

Tables of key patient information for SAEs and AEs leading to discontinuation of study medication will be provided. Adverse events will be listed.

The number of AEs and number of SAEs will be summarized for the controlled assessment period and extension period.

The denominator for summaries will be the number of patients included in the analysis set by treatment group and total. Where the controlled assessment period and extension period are presented side-by-side in the same summary, the denominator for the controlled assessment period will be the number of patients in the Safety analysis set by treatment group and total; the denominator for the extension period will be the number of patients in the subset of Safety patients who received open-label EQW during the extension period by treatment group and total.

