12.6.7.1 Adverse events

On treatment AEs will be defined as those occurring after the first administration of study medication on Visit 2 (Week 0) through Study Termination or Early Termination or after Study Termination but considered by the Investigator as clinically significant and as related to study medication or study procedure; or an SAE reported within 90 days of the last administration of EQW; or existing prior to the time of and worsening after the time of the first administration of study medication. Adverse events prior to the first administration of study medication on Visit 2 (Week 0) will be classified as pretreatment

(non-treatment-emergent). Detailed rules for classification of on treatment AEs in the extension period will be specified in the SAP.

On treatment AEs will be summarized by treatment, system organ class, and preferred term defined by MedDRA. The number of events, the number of patients, and the percent of patients who experienced at least 1 on treatment AE will be presented for each system organ class and for each preferred term by treatment group. On treatment AEs that are related to study medication, on treatment AEs that lead to early withdrawals, and serious on treatment AEs will be summarized in the same manner.

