3.6.5.2 Safety and concomitant medications

Adverse events, hypoglycemic events and concomitant medications on the date of first dose of open-label EQW (Week 24 visit) will be assigned to the extension period as this is considered a conservative approach. Other safety assessments at the Week 24 visit will be considered to have been carried out pre-dose and will therefore be assigned to the controlled assessment period. This is reflected in the definitions below.

Controlled assessment period:

- For patients who do not enter the extension period, the controlled assessment period will be defined as date of first dose of randomized study medication to date of last dose of randomized study medication + 7 days (or + 90 days after last dose of study medication for reporting of serious adverse events (SAEs) and other clinically significant or related AEs).
- For patients who go on to enter the extension period, the controlled assessment period for all safety parameters except AEs, hypoglycemic events and concomitant medications will be defined as date of first dose of randomized study medication to date of first dose of open-label EQW. For AEs, hypoglycemic events and concomitant medications, the controlled assessment period will be defined as date of first dose of randomized study medication to date of the first dose of open-label EQW – 1 day, in order for AEs, hypoglycemic events and medications recorded on the date of first dose of open-label EQW to be assigned to the extension period.

Extension period: For all safety parameters, except AEs, hypoglycemic events and concomitant medications, the extension period will be defined as date of first dose of open-

label EQW + 1 to date of last dose of open-label EQW + 7 days. For AEs, hypoglycemic events and concomitant medications, the extension period will be defined as date of first dose of open-label EQW to date of last dose of open-label EQW + 7 days (or + 90 days for SAEs and other clinically significant or related AEs). The extension period will only be defined for patients who enter the extension period and receive at least one dose of open-label EQW.

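### The SAP's treatment-emergent AE rules omit the protocol's worsening exception and, for patients who stop drug before the extension, end the window for other AEs at last dose + 7 days; SAP Section 5 declares neither

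*SAP*

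**What the plan says.** **Protocol 12.6.7.1.** An on-treatment AE is one occurring "after the first administration of study medication on Visit 2 (Week 0) through Study Termination or Early Termination". Three groups are added: AEs after Study Termination that the investigator judges both clinically significant and related; SAEs reported within 90 days of the last EQW dose; and events "or existing prior to the time of and worsening after the time of the first administration of study medication". Other AEs before first dose are pretreatment. One matter is left to the SAP: "Detailed rules for classification of on treatment AEs in the extension period will be specified in the SAP".

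**SAP.** Section 4.2.4.1 takes TEAEs from first dose "through the end of the treatment plus 7 days (or + 90 days for SAEs and other clinically significant or related AEs"). For patients who do not enter the extension, Section 3.6.5.2 defines the controlled period as "date of first dose of randomized study medication to date of last dose of randomized study medication + 7 days", with the same 90-day provision. For patients who do enter, the controlled period for AEs ends the day before the first open-label dose. Section 4.2.4.1 also states: "AEs with a start date prior to the first administration of study medication will be classified as pre-treatment (non-treatment emergent"). It gives no exception for worsening. AEs beyond the window are off-treatment. For Week 52 completers they are tabulated where required; for the rest, "Off-treatment AEs for patients who prematurely discontinued will be listed only".

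SAP Section 5 records many changes from the protocol, including a new safety analysis set and added hypoglycemia summaries. It mentions neither the AE window nor worsening. The SAP amendment history describes the TEAE windows only as clarified between SAP versions.

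**The concern.** Safety and tolerability against placebo over 24 weeks is one of the two primary objectives, and TEAE incidence is the main way it is reported. The two documents define that quantity differently, and a reader who relies on Section 5 to learn what changed would not find out. The arms are small, so reclassifying even one patient visibly moves an incidence. AEs that fall outside the window in early stoppers leave the by-arm tables and appear only in a listing, where they cannot be compared between arms.

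**Working it through.** No power or alpha figure is involved. The check is a comparison of texts plus day and percentage arithmetic.

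**1. What was delegated.** Protocol 12.6.7.1 hands over extension-period classification only. That covers the SAP's rules after open-label EQW, including its separate handling of Week 52 completers. It does not cover patients who never enter the extension, nor the worsening rule.

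**2. Worsening, case by case.** AEs are collected from consent (Protocol 6.4.3), and up to 35 days may pass between screening and first dose, so events can begin before dosing.

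- *Ended before first dose:* pre-treatment under both documents.
- *Post-dose deterioration entered as its own AE:* Protocol 6.4.1 makes deterioration of a pre-existing condition an AE. The record has a post-dose start and is counted at patient level under both. For event counts, SAP 4.3.4.3 merges contiguous or overlapping records of the same preferred term and keeps the earliest onset date. If TEAE status is set after merging, the worsening reverts to pre-treatment. The SAP does not state the order.
- *One record spanning first dose:* counted by the protocol if it worsened, pre-treatment under the SAP. The AE variables in Protocol 6.4.3 include start and stop dates and maximum intensity but no date of worsening, so the data alone cannot recover it.

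**3. Window end, and for whom.** For extension entrants the controlled period ends before the first open-label dose, so + 7 days does not touch their part of the 24-week comparison. That leaves patients who stop in the controlled period and do not enter the extension. Let d be the days from last dose to Early Termination. For AEs that are not serious, clinically significant or related:

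protocol window end − SAP window end = d − 7

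| d (illustrative) | Result |
|---|---|
| 3 | −4: SAP window 4 days longer |
| 7 | 0: same |
| 14 | +7: SAP window 7 days shorter |
| 28 (one 4-week visit gap) | +21: SAP window 21 days shorter |

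SAP 3.6.3 has patients invited as soon as possible, which points to small d, but it is only an invitation. SAP 3.6.5.4 and 4.2.3.3 both provide for patients who are off drug and still on study. The documents do not give the distribution of d.

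**4. The 90-day provision.** After termination the protocol requires a non-serious AE to be clinically significant *and* related; the SAP accepts *or*. On paper the SAP is broader here. How much this adds is limited, because Protocol 6.4.3 asks sites to record non-serious AEs after termination procedures only when both conditions hold.

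**5. Weight of one patient.** Assume all 77 are dosed at exactly 5:2.

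- Arms: 77 × 5/7 = 55 EQW; 77 × 2/7 = 22 placebo.
- One patient: 1/55 = 1.8 points; 1/22 = 4.5 points.
- The SAP has a table of "Frequent AEs (AE with at least 5% incidence in any treatment) summarized by preferred term". One added patient can take a term over that line: placebo 1/22 = 4.5% to 2/22 = 9.1%; EQW 2/55 = 3.6% to 3/55 = 5.5%.

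This is the effect of one reclassified patient, not an estimate of how many there are.

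**The case against.** The strongest reply is that a window tied to last dose is a legitimate analysis choice and that little is lost. SAEs and clinically significant or related AEs run to + 90 days, AEs leading to discontinuation are reported whatever their date, and every AE is listed. A missing seriousness or causality rating is set to the worse category. The planned path for an early stopper is a prompt Early Termination visit and then, for most, Extended Safety Follow-up, where only AEs of special interest are recorded. The 5% line is presentational, since all TEAEs are tabulated by SOC and preferred term and no decision depends on it. All of this stands, and it keeps the point modest.

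It can also be said that the protocol itself classes AEs before first dose as pretreatment, so the SAP merely repeats it. This does not hold: in the protocol that sentence follows an explicit inclusion of worsened events, and the SAP kept the one without the other. SAP 4.2.4.1 does define AEs for the combined periods, including post-treatment events, but the summaries listed there name no by-arm table that uses this set.

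Two stronger readings are tempting. A reader might infer that the SAP simply shortens follow-up and so flatters EQW. The documents do not support this: the window can be shorter or longer, and nothing shows which arm would gain. A reader might also count the follow-up of Week 52 completers as lost, because Visit 11 falls 70 to 84 days after final dose, which is 63 to 77 days past the SAP cut-off. But those are extension-period rules that the protocol delegated, and the SAP provides for tabulating these events separately.

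**Conclusion.** The point holds within these limits. The SAP departs from Protocol 12.6.7.1 in two ways that Section 5 does not declare: it omits the worsening exception, and for controlled-period early stoppers it replaces Early Termination with last dose + 7 days for AEs that are not serious, clinically significant or related. Outside the extension neither change was delegated, and the worsening exception was not delegated at all. The SAP window is shorter only when Early Termination comes more than 7 days after last dose or does not occur.

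The number of events or patients affected and the direction of any effect cannot be computed from the documents. The 1.8 and 4.5 points per patient rest on 77 patients dosed at exactly 5:2. The matter should be corrected because it bears on a primary objective in small arms and is cheap to put right. It is not evidence that the safety comparison is biased.

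**What to change.** - **Worsening.** In SAP 4.2.4.1, restore the protocol's exception. Identify such events from separate post-dose records and from blinded review or query of single records that span first dose.
- **Order of steps.** State that TEAE status is assigned before records are merged under 4.3.4.3.
- **Early stoppers.** For patients who do not enter the extension, tabulate AEs by arm from first dose through Early Termination, capped at the Week 24 visit (Day 169), alongside the + 7-day table. Without the cap, a patient off drug but still on study would have a controlled period with no end at Week 24.
- **Leave alone.** Keep the extension-period rules and the off-treatment rules for Week 52 completers.
- **Section 5.** Record and justify any departure from Protocol 12.6.7.1 that remains.

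Cost: SAP wording, blinded review or query of the spanning records, and a re-run of the AE tables. No new visits or assessments are needed.
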